## **Subject Retention:**

We will remind participants of outlined program events/milestones at multiple time points during recruitment, assessment and after randomization to support our retention efforts and to reiterate requirements of the study to participants. The communication plan for reminders will include a variety of means of contact (i.e. church announcements, flyers, telephone calls and automated emails). These strategies have enhanced our adherence/retention rates to interventions and health assessments in prior studies. In addition, there will be mandatory meetings with the study team at Mayo Clinic and collaborating sites to discuss progress and problem solve issues related to retention and data collection. Quarterly FAITH! CSC meetings will also review these items in detail to inform any necessary protocol modifications.

## **Subject Participation Remuneration:**

### **Aim 1**

Participants will receive a total of \$100 by Visa gift card (\$50 at enrollment, \$50 at completion) and a personal PA monitor (i.e. Fitbit). Participants are only eligible to participate within this phase of the proposed project (i.e. focus group series only).

### **Aim 2: Churches**

Churches are not considered subjects in FAITH! Trial, but it is worth mentioning that churches completing the screening survey will receive a health ministry starter kit by mail. Churches meeting our screening and inclusion criteria as well as signing a letter of mutual intent will receive a \$250 incentive for committing to participate in the study (goal distribution to church by completion of intervention post-maintenance phase for respective study arm).

### **Aim 2: Participants**

Participants will receive a total of \$150 by Visa gift card (\$50 at enrollment, \$50 at immediate post-intervention and \$50 at 6-months follow-up), a cookbook with healthy recipes, a Mayo Clinic-published heart healthy book along with a personal PA monitor (FitBit). Participants who are selected to participate in optional group meeting will receive a \$50 cash card at the conclusion of the meeting.

## **Dissemination Plan:**

We have identified five key audiences for dissemination of our research findings which include the following:

- 1. FAITH! CSC**
- 2. Partnering AA churches (Rochester and MSP, MN)**
- 3. Local AA community (Rochester and MSP, MN)**
- 4. State-wide to regional public health organizations (e.g. Olmsted County and Minnesota Departments of Health, Midwest local affiliate AHA)**
- 5. Academia (nationally and internationally)**

To ensure that the findings from our research informs community level health interventions to promote CV health and thereby maximizing the benefit to underserved AA communities, the following dissemination strategy has been developed by the study team:

First, the PI ([name]) and study consultant ([name]) will formally co-present an executive summary of the study primary and secondary outcome findings to the FAITH! CSC at a regularly scheduled quarterly meeting, not only as an informative session but to also receive feedback and advice on the most

appropriate dissemination plans at the local, state and national levels. The study team will utilize this feedback to further inform and strengthen the dissemination strategy.

Second, the next audience for dissemination is the partnering AA congregations which encompass the church leadership, FAITH! Partners and last but not least--the study participants. We will hold at least three faith community-wide events (one in each city-Rochester, Minneapolis, St. Paul) at the end of the study to provide the overall results in a clear and succinct manner with incorporation of slide and video presentations and culturally appropriate infographics. As outlined in the Overall Strategy and Design section, the top-ranked church for highest levels of tracked fruit/vegetable intake and PA (by the app thermometer goal chart) will be acknowledged. In addition, a FAITH! Program-specific newsletter (paper and digital) will be created to provide ongoing updates about research plans, publications and church/participant testimonials.

Next, at the local AA community level, we will hold two community-wide outreach events (one in Rochester and one in MSP) to promote ideal CV health in the form of a "Walk by FAITH!" 5K event which will start and end with testimonials from the study team, FAITH! CSC and partnering church leadership on the importance of healthy lifestyle practices. We will also capitalize on social media (i.e. Facebook, Twitter), local newspapers (including *Minnesota Spokesman-Reporter*, *Insight News*) and radio shows ([name] weekly radio program, *Community Health Dialogues*, KMOJ FM Radio, Minneapolis) for proactive dissemination of our study findings to our prioritized population.

On a statewide level, the PI and [name] will jointly present executive summaries of the FAITH! mHealth intervention components and study findings to key influential organizations to inform health policy, environmental and systems change in the Rochester and MSP areas (Departments of Health and local-affiliate AHA). Two of our FAITH! CSC members are closely aligned as leadership and stakeholders within these organizations and will be fully engaged to ensure that robust and actionable recommendations are generated to maximize their uptake. Central to our meetings with these organizations are to identify the potential benefits/role of the FAITH! intervention and program as a whole in improving the CV health of MN AA communities as a part of ongoing community-based programming within these entities. As a reciprocal dialogue, we also hope to collaboratively assess the quality of the current community health programs and services in meeting the needs and priorities of the AA community and how the FAITH! Program can assist in transforming program delivery models and facilitating ideal CV health outcome benchmarking.

Lastly, the PI, Co-Is and community partners will present study findings within academia both nationally and internationally. Anticipated conferences include the following: AHA Scientific Sessions, AHA Epidemiology, American Public Health Association Annual Meeting, AcademyHealth, European Cardiology Society, American Society of Preventive Cardiology and the Mixed Methods International Research Association Global Conference. This level of dissemination also includes peer-reviewed publications in high impact academic journals and research summaries for professional journals all written and co-authored with our community partners. The PI will ensure that the study is registered and that its results are submitted to ClinicalTrials.gov in compliance with NIH specific timelines and policies and our own institutional policy at Mayo Clinic. All informed consent documents will include a specific statement relating to posting of information related to this study at ClinicalTrials.gov. The lessons learned from our research can be translated and adapted to other racial/ethnic minority groups and underserved populations to enhance efforts to effectively promote CV health.

**Resources:** *Describe the available resources to conduct the research (personnel, time, facilities, mentor commitment, etc.):*

### **CSC:**

As infrastructure for the overarching CBPR partnership for CV health promotion within the AA community, a FAITH! Program-specific CSC was established including 10 members from diverse community organizations in MN. It will inform all research phases, meet quarterly with the study team, and receive an honorarium.

- (1a) This is a multisite study involving Mayo Clinic and non Mayo Clinic sites. *When checked, describe in detail the research procedures or activities that will be conducted by Mayo Clinic study staff.*

### **Locations:**

Mayo Clinic study staff will be the lead coordinating center, and responsible for oversight of study conduct, training appropriate personnel, communication, facilitating the use of the most current and IRB approved study processes, subject recruitment and data analysis.

- (1b) Mayo Clinic study staff will be engaged in research activity at a non Mayo Clinic site. *When checked, provide a detailed description of the activity that will be conducted by Mayo Clinic study staff.*

Please see the methods for additional information on the inclusion of community partners.

### **Subject Information**

*Target accrual is the proposed total number of subjects to be included in this study at Mayo Clinic. A "Subject" may include medical records, images, or specimens generated at Mayo Clinic and/or received from external sources.*

**Target accrual:** 215 participants

Aim 1: 15 participants

Aim 2: 16 churches, 200 participants

**Subject population (children, adults, groups):**

Adult community members affiliated with the partnering AA churches in Rochester and MSP, MN

### **Inclusion Criteria:**

#### **Aim 1**

- Men and women 18 years of age and older
- AA race/ethnicity

- Basic Internet navigation skills
- Active email address

#### **Aim 2: Churches**

- predominantly AA parishioners
- church size >50 members
- commitment from church pastor/senior leadership to promote the study at church
- willingness of church member to serve as church liaison (FAITH! Partner)

#### **Aim 2: Participants**

- Men and women 18 years of age and older
- AA race/ethnicity
- Basic Internet navigation skills (at least weekly access)
- Active email address
- Ownership of smartphone (supporting iOS or Android systems)
- Minimal fruit/vegetable intake (<5 servings/day)
- No regular PA program (<30 minutes/day of moderate PA)
- Able to engage in moderate PA (such as brisk walking, dancing, aerobics, gardening, weight lifting without restrictions including physical disability, use of a wheelchair daily or serious medical condition)

#### **Exclusion Criteria:**

##### **Aim 1**

- Unable to commit to participating in at least 3 focus groups over 3 month period.
- Have visual/hearing impairment or mental disability that would preclude independent use of the app.

##### **Aim 2**

- Unable to walk up at least two flights of stairs or walk at least one city block without assistance or stopping
- Pregnant or planning to become pregnant within 2 years (due to associated hormonal and weight changes)
- Have visual/hearing impairment or mental disability that would preclude independent use of the app.
- Participant in Aim 1 focus groups

#### **Research Activity**

Check all that apply and complete the appropriate sections as instructed.

1.  **Drug & Device:** Drugs for which an investigational new drug application is not required. Device for which (i) an investigational device exemption application is not required; or the medical device is

cleared/approved for marketing and being used in accordance with its cleared/approved labeling. (Specify in the Methods section)

2.  **Blood:** Collection of blood samples by finger stick, heel stick, ear stick, or venipuncture.
3.  **Biological specimens other than blood:** Prospective collection of human biological specimens by noninvasive means that may include: urine, sweat, saliva, buccal scraping, oral/anal/vaginal swab, sputum, hair and nail clippings, etc.
4.  **Tests & Procedures:** Collection of data through noninvasive tests and procedures routinely employed in clinical practice that may include: MRI, surface EEG, echo, ultrasound, moderate exercise, muscular strength & flexibility testing, biometrics, cognition testing, eye exam, etc. (Specify in the Methods section)
5.  **Data** (medical record, images, or specimens): Research involving use of existing and/or prospectively collected data.
6.  **Digital Record:** Collection of electronic data from voice, video, digital, or image recording. (Specify in the Methods section)
7.  **Survey, Interview, Focus Group:** Research on individual or group characteristics or behavior, survey, interview, oral history, focus group, program evaluation, etc. (Specify in the Methods section)

NIH has issued a *Certificate of Confidentiality* (COC). *When checked, provide the institution and investigator named on the COC and explain why one was requested.* \_\_\_\_\_

#### **Biospecimens – Categories 2 and 3**

(2) Collection of blood samples. When multiple groups are involved copy and paste the appropriate section below for example repeat section b when drawing blood from children and adults with cancer.

- a. **From healthy, non-pregnant, adult subjects who weigh at least 110 pounds.** For a minimal risk application, the amount of blood drawn from these subjects may not exceed 550ml in an 8 week period and collection may not occur more frequently than 2 times per week.

Volume per blood draw: Fingerstick blood sample only (per lipid panel, glucose sample)

Frequency of blood draw (e.g. single draw, time(s) per week, per year, etc.) Once at baseline assessment and 6-months follow-up assessment

#### **Review of medical records, images, specimens – Category 5**

**For review of existing data:** provide a date range or an end date for when the data was generated. The end date can be the date this application was submitted to the IRB. Example: *01/01/1999 to 12/31/2015* or all records through *mm/dd/yyyy*.

#### Date Range:

Check all that apply (data includes medical records, images, specimens).

- (5a) Only data that exists before the IRB submission date will be collected.
- (5b) The study involves data that exist at the time of IRB submission **and** data that will be generated after IRB submission. Include this activity in the Methods section.

#### Examples

- The study plans to conduct a retrospective chart review and ask subjects to complete a questionnaire.
- The study plans to include subjects previously diagnosed with a specific disease and add newly diagnosed subjects in the future.

- (5c) The study will use data that have been collected under another IRB protocol. Include in the Methods section and enter the IRB number from which the research material will be obtained. *When appropriate, note when subjects have provided consent for future use of their data and/or specimens as described in this protocol.*

Enter one IRB number per line, add more lines as needed

- Data    Specimens    Data & Specimens \_\_\_\_\_
- Data    Specimens    Data & Specimens \_\_\_\_\_
- Data    Specimens    Data & Specimens \_\_\_\_\_

- (5d) This study will obtain data generated from other sources. Examples may include receiving data from participating sites or an external collaborator, accessing an external database or registry, etc. Explain the source and how the data will be used in the Methods section.

- (6) Video audio recording: *Describe the plan to maintain subject privacy and data confidentiality, transcription, store or destroy, etc.*

#### HIPAA Identifiers and Protected Health Information (PHI)

Protected health information is medical data that can be linked to the subject directly or through a combination of indirect identifiers.

Recording identifiers (including a code) during the conduct of the study allows you to return to the medical record or data source to delete duplicate subjects, check a missing or questionable entry, add new data points, etc. De-identified data is medical information that has been stripped of all HIPAA identifiers so that it cannot be linked back to the subject. De-identified data is **rarely** used in the conduct of a research study involving a chart review.

**Review the list of subject identifiers below and, if applicable, check the box next to each HIPAA identifier being recorded at the time of data collection or abstraction.** Identifiers apply to any subject enrolled in the study including Mayo Clinic staff, patients and their relatives and household members.

**Internal** refers to the subject's identifier that will be recorded at Mayo Clinic by the study staff.

**External** refers to the subject's identifier that will be shared outside of Mayo Clinic.

Check all that apply:	INTERNAL	EXTERNAL
Name	X	
Mayo Clinic medical record or patient registration number, lab accession, specimen or radiologic image number	X (Aim 2)	
Subject ID, subject code or any other person-specific unique identifying number, characteristic or code that can link the subject to their medical data	X	
Dates: All elements of dates [month, day, and year] directly related to an individual, their birth date, date of death, date of diagnosis, etc.	X	
Note: Recording a year only is not a unique identifier.		
Social Security number	X	
Medical device identifiers and serial numbers		
Biometric identifiers, including finger and voice prints, full face photographic images and any comparable images		
Web Universal Resource Locators (URLs), Internet Protocol (IP) address numbers, email address	X	
Street address, city, county, precinct, zip code, and their equivalent geocodes	X	
Phone or fax numbers	X	
Account, member, certificate or professional license numbers, health beneficiary numbers		
Vehicle identifiers and serial numbers, including license plate numbers		
Check 'None' when none of the identifiers listed above will be recorded, maintained, or shared during the conduct of this study. (exempt category 4)	 None	 None

#### Data Analysis

*Power analyses may not be appropriate if this is a feasibility or pilot study, but end-point analysis plans are always appropriate even if only exploratory. Provide all information requested below, or provide justification if not including all of the information.*

## **Power Statement:**

### **Aim 1**

**Not applicable.**

### **Aim 2**

The primary outcome will be a comparison of average change in the AHA LS7 score from baseline (Time 1) to 6-months post-intervention (Time 3) between Groups 1 and 2. Based on our prior study of 37 participants, including 5 churches, the intracluster correlation (ICC) of this outcome was near zero (<0.01), and the coefficient of variation (CoV) of church sizes was 0.38 (average number of participants/church, 10; SD 3.8; CoV 0.38). Assuming similar ICC (0.01) and slightly higher CoV (0.50) since more churches will be included in the planned study, including a total of 16 churches with an average of 10 participants/church, 80 participants/group will provide 85% power to detect a difference of 1.0 in average LS7 score change between the groups (SD 2; effect size 0.50; 5% type-I error rate). The clinical significance of this 1-unit difference in LS7 score is based on a recent meta-analysis demonstrating that each unit increase in LS7 metrics is associated with an estimated 19% and 11% reduction in CVD and all-cause mortality respectively. We will recruit 200 participants to ensure 160 completers (assuming 20% attrition rate).

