**Schedule of Assessments**

Data Collected	# Items	Baseline	Immediate Post-intervention	6 months
Sociodemographics				
eHealth literacy: eHEALS 	10	X		
Mobile technology use skills 	13	X		
CV health (LS7) measures				
BP	--	X		X
Fasting lipid panel	--	X		X
Fasting glucose	--	X		X
Height/weight (BMI)	--	X		X
Cigarette smoking status	--	X		X
Diet quality: Delta Nutrition Intervention FFQ 	158	X	X	X
PA patterns: International PA Questionnaire 	7	X	X	X
Feasibility measures				
App engagement	--		X	X
App usability 	20		X	X
Psychosocial measures				
Diet/PA self-efficacy 	12/12	X	X	X
Diet/PA self-regulation 	16/10	X	X	X
Diet/PA social support 	10/13	X	X	X
Religiosity/spirituality: Daily Spiritual Experiences Scale 	6	X		X
Optimism: Life Orientation Test-Revised 	6	X		X
Perceived stress: Global Perceived Stress Scale 	8	X		X

**Randomization (Figure 2).** We will use a cluster RCT design with 2 waves of implementation inclusive of 2 groups: intervention (Group 1) and delayed intervention (Group 2, control group). We will randomize clusters of churches in Rochester and MSP to receive the intervention immediately following baseline health assessments including LS7 measures (Time 1, Group 1) or at post-maintenance (Time 3, Group 2). Groups 1 and 2 will complete post-intervention assessments by electronic survey of CV health behaviors, feasibility and psychosocial measures (Times 2 and 4). Both groups will complete a second health assessment at post-maintenance (Time 3), to allow for comparison of LS7 measures between Groups 1 and 2. Times 4 through 5 are data collection points following the intervention (post-intervention and post-maintenance) for Group 2. The study statistician will randomize churches, ensuring the number of participants in Groups 1 and 2 is balanced. Churches will be told their group assignment after baseline assessments.

[figure not shown]

Figure 2. RCT with delayed intervention

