### **Aim 2**

Study measures will be summarized and compared between groups using  $\chi^2$  tests for categorical variables and 2-sample *t*-tests for continuous variables. Differences between baseline and each follow-up will be calculated for continuous measures. These differences will be examined overall and within each group, with paired *t*-tests. The average change from baseline will be compared between intervention and control groups with 2-sample *t*-tests. The distribution of categorical outcomes (eg, LS7 component category: poor, intermediate, ideal) will be compared between baseline and each follow-up with McNemar's tests. All variables will be assessed and reported by sex.

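### The stated 85% power at 5% error relies on a large-sample critical value; a size-weighted church-level test of 16 churches (14 df) has about 80%, and the plan names no church-respecting analysis

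*Combined protocol and SAP*

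**What the plan says.** The Power Statement (Aim 2) defines the primary outcome as the between-group difference in LS7 score change from baseline to 6 months post-intervention. It claims that "80 participants/group will provide 85% power to detect a difference of 1.0 in average LS7 score change between the groups", based on 16 churches averaging 10 participants each. The remaining inputs to that claim are listed as "SD 2; effect size 0.50; 5% type-I error rate".

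Clustering is allowed for in that figure: "Assuming similar ICC (0.01) and slightly higher CoV (0.50) since more churches will be included in the planned study". The ICC comes from earlier work: "Based on our prior study of 37 participants, including 5 churches, the intracluster correlation (ICC) of this outcome was near zero (<0.01"). Church sizes in that work are summarised as "average number of participants/church, 10; SD 3.8; CoV 0.38". The test, its sidedness and its degrees of freedom are not stated.

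The Randomization paragraph under Schedule of Assessments makes the church the unit: "We will randomize clusters of churches in Rochester and MSP to receive the intervention immediately following baseline health assessments including LS7 measures". It adds: "The study statistician will randomize churches, ensuring the number of participants in Groups 1 and 2 is balanced".

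The Data Analysis Plan (Aim 2) gives the comparison as follows: "The average change from baseline will be compared between intervention and control groups with 2-sample" t-tests. It mentions no church term, weighting or cluster-level degrees of freedom.

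**The concern.** A reader will take 85% as the power of a valid 5% test of church-randomised groups on the primary outcome. The power calculation inflates the variance for clustering but appears to refer the result to a normal distribution, as if the variance were estimated from many independent units. With 16 churches, a test that estimates between-church variation from the churches themselves has few degrees of freedom and a larger critical value.

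The analysis section does not settle the matter, because its t-test ignores church altogether. One section treats clustering as worth adjusting for and the other leaves it out, so the 85% belongs to no named test. At stake are the accuracy of the stated power and the type I error of the primary comparison. The size of the trial is not in question.

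**Working it through.** **Inputs (Power Statement, Aim 2).** Difference 1.0; SD 2; 80 completers per group; mean church size m = 10; 16 churches; ICC 0.01; CoV 0.50; type I error 5%. Two-sided testing is inferred: a one-sided 5% normal test would give 91.2%, which does not match.

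**Step 1: reproduce the plan's figure.**
- Design effect = 1 + ((1 + CoV²)m - 1) × ICC = 1 + (1.25 × 10 - 1) × 0.01 = 1.115.
- Noncentrality = 1 / (2 × √(2 × 1.115 / 80)) = 2.995.
- Two-sided power with a normal critical value = 85.0%. The stated figure reproduces.

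**Step 2: same noncentrality, different reference distribution.** A church-level test of 16 churches has 16 - 2 = 14 df however the churches are split between groups; its critical value is 2.145.

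| Reference | Power |
|---|---|
| Normal | 85.0% |
| t, 158 df (participants) | 84.5% |
| t, 60 df | 83.8% |
| t, 30 df | 82.6% |
| t, 20 df | 81.3% |
| t, 14 df (churches) | 79.5% |

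On 14 df, the difference detectable with 85% power is 1.08. A mixed model with intermediate df lies between about 80% and 84.5%.

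**Step 3: does the plan's margin close the gap?** On 14 df, with ICC 0.01 and the prior study's CoV of 0.38, power is 79.9%. With ICC 0 (design effect 1) it is 83.6%, still below 85%. The shortfall comes from the reference distribution, not from cautious inputs.

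**Step 4: simulation.** 100,000 runs per cell; 80 participants per arm in 8 churches; gamma-distributed church sizes (minimum 2) with realised CoV 0.50; total SD 2. ICCs above 0.01 are assumptions. Each cell shows power, then type I error.

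| Test | ICC 0.01 | ICC 0.02 | ICC 0.05 |
|---|---|---|---|
| Size-weighted church-level t, 14 df | 80.4%, 0.053 | 77.1%, 0.055 | 68.6%, 0.060 |
| Unweighted church means t, 14 df | 70.3%, 0.048 | 67.8%, 0.048 | 60.8%, 0.048 |
| Participant-level t, 158 df | 86.9%, 0.064 | 85.8%, 0.076 | 83.1%, 0.119 |

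Splitting the churches 7/9 or 6/10, with 80 participants still in each group, leaves the size-weighted result at ICC 0.01 essentially unchanged (80.4% and 80.2%).

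**Step 5: analytic sensitivity on 14 df (assumed ICCs).** ICC 0.02: design effect 1.230, noncentrality 2.851, power 75.5%. ICC 0.05: design effect 1.575, noncentrality 2.520, power 65.0%. The simulated size-weighted power at ICC 0.05 is a little higher (68.6%), partly because that test then runs slightly above 5% error.

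**Step 6: baseline adjustment.** Take a score SD of 2.1 at both visits (Table 1, LS7 composite score) and a change SD of 2. The implied correlation is 1 - 4 / (2 × 2.1²) = 0.546. Noncentrality becomes 2.995 / √((1 + 0.546) / 2) = 3.406, and power on 14 df is 88.6%, with the ICC held at 0.01.

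**Side check.** 37 participants in 5 churches average 37 / 5 = 7.4, not the stated 10. Dividing the stated SD by that mean gives 3.8 / 7.4 = 0.51, close to the planned CoV of 0.50, so the power is not affected.

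**The case against.** The strongest reply is that nothing was miscalculated. The 85% follows from the stated inputs, the ICC and unequal church sizes are already included, and the 14-df test is the reviewer's choice, since the plan names no cluster analysis. This is correct as far as it goes. It also describes the problem: a power figure has to belong to a test, and the one test the plan names does not hold 5%.

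The answer does depend on the test chosen. A mixed model could reach up to about 84.5%, and a baseline-adjusted church-level analysis about 89% under the assumptions in Step 6. That stands, and it is a reason to name the analysis.

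The 70% for unweighted church means rests on the planned CoV of 0.50. The recruitment sections ask for a minimum of 10 participants per church, and 200 / 16 = 12.5 on average, so sizes may vary much less. Simulating such a floor with 20% random attrition raises the unweighted test to about 79%. The 70% should be read with that condition. Under the same floor the size-weighted test stays at about 80%, and the participant-level t-test still has an error of about 0.061.

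The size-weighted test is itself slightly above 5% (0.053 at ICC 0.01 with CoV 0.50). The excess is small, but it is real.

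Finally, this is a feasibility and preliminary-efficacy trial, 80% is a conventional target, and the larger error rates need ICCs above the one observed. All of that limits the consequence. It does not make 85% at 5% error correct for the primary outcome, and an ICC estimated from 37 participants in 5 churches cannot rule out higher values.

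**Conclusion.** The concern holds. At the plan's own inputs, a size-weighted church-level test of the unadjusted change score has about 80% power, roughly 5.5 points below the 85% stated. The planned participant-level t-test exceeds the stated error rate (about 0.06 at ICC 0.01, more if the ICC is larger). None of the unadjusted tests examined gives both 85% power and 5% error.

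The result assumes two-sided testing, 80 completers per group and inference on 14 df; the simulated figures also assume gamma-distributed church sizes. The shortfall is modest, and it concerns the stated figure and the unnamed analysis behind it. The mismatch between 10 and 7.4 participants per church in the prior study is a separate inconsistency with no effect on power.

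**What to change.** - **Data Analysis Plan, Aim 2:** name a primary analysis that respects church, with its weighting and degrees of freedom; for example, a size-weighted church-level t-test on 14 df.
- **Power Statement, Aim 2:** restate the power for that analysis: about 80% (two-sided 5%, 14 df, size-weighted, ICC 0.01, CoV 0.50, unadjusted change), or a detectable difference of 1.08 at 85% power.
- **Sensitivity:** add a short table with the ICCs labelled as assumptions: 79.5% at 0.01, 75.5% at 0.02, 65.0% at 0.05.
- **If baseline adjustment is preferred:** adopt it within a church-respecting analysis and state its power with the assumed correlation and SDs (about 89% at ICC 0.01, with score SD 2.1 and correlation about 0.55).
- **Prior study:** reconcile the stated mean of 10 per church with 37 / 5 = 7.4.

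The cost is one sentence, one reworded paragraph and a small table. No churches or participants are added. The only drawback is that the stated power falls from 85% to about 80% unless the adjusted analysis is adopted.
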